## **Data Management**

Data management is the responsibility of the student investigators and the outreach coordinator. The key outcome measures are all recorded automatically and electronically. This includes pill bottle openings and SteadyRx use measures. All participants will be trained to the point of skill mastery on all aspects of using the electronic pill bottles and the SteadyRx system. The data for all ACASI assessments will be stored in the Qualtrics database. The data for all MEMS caps readings will be stored within the medAmigo database. The data for all PillWatch

assessments will be stored in the backend of the SteadyRx application. All data will be stored on the SteadyRX server. With respect to the SteadyRX system servers, these Servers have been hardened against attack over the network and an intrusion detection system is in place. Administrative access to servers is by encrypted, private key-secured channels only. Servers are physically secured in a locked cabinet in a locked room in a secure facility accessible by photo ID only. The computer services provided under this project include daily system-wide on-site and encrypted offsite backups with incremental database backups in 15 minute intervals. All data transfer will be encrypted using 256-bit SSL encryption, the standard level of encryption used to secure eCommerce and banking transactions on the Internet. HIV serostatus and viral load measures, and drug use history will be provided by the participants' doctor and transmitted over the phone by the outreach coordinator to the WMU staff. A log of the materials assigned to the participants and a discharge log will also be kept on Google Drive.

All video submission data from those in the SteadyRx group will be recorded on individual google sheets. Submissions (y/n), time of submission, submission acceptances, money earned and when payments are made are included in the Google Sheets. Videos are independently accepted or rejected by two student investigators (see [Assessing Videos in SteadyRx](#)).

ALL of these databases will be transcribed to a master Google Sheet excel file on a regular basis. In order to ensure accuracy in transcription of paper based data (e.g., HIV serostatus and viral load), two investigators will transcribe the data separately and it will only be recorded on the master data sheet upon agreement. The responsibility of updating these excel files will be shared between the student investigators and the outreach coordinator. Data will be backed up on one of two external hard drives on a weekly basis. Hard drives used will be alternated and the responsibility will be shared across student investigators.

## MAIN STUDY DISCHARGE

Main Study Discharge will occur for all participants irrespective of group assignment upon completion of the 6th Main Study Assessment and should be scheduled for study day 180. Outreach staff are responsible for Main Study Discharge and should follow the [Discharge Checklist](#). The Main Study Discharge interview is identical to the monthly assessment interview aside from collecting the participant's smartphone and MEMS cap. The participant is entitled to a \$100 incentive for keeping the same smartphone for the entire study period and returning it during this interview. Alternatively, they can forego the \$100 and keep the smartphone. They will be told of this choice during the intake interview and reminded at study discharge. If they choose to keep the phone, immediately remove payment and contact information from the Boost Mobile account. Also change the pin to their participant ID and make a note in the phone number records log.

### **Analytic plan for SteadyRx study**

Descriptive statistics (means and standard deviations or proportions) will be calculated for demographics, baseline participant factors (e.g., quality of life, substance use), treatment history, health literacy, and application ratings and engagement. All analyses will be intent to treat; all participants who are randomized will be included. All analyses will be adjusted for the pre-specified covariates used for stratification. All hypothesis tests will be two-sided,  $\alpha$  will be set at 0.05, and p-values for secondary analyses will be corrected to maintain  $\alpha=0.05$ . Based on our past research and the automated collection of our primary outcome measure, we expect relatively little missing data and little difference in the rates of missing data across groups. We plan to conduct analyses in which missing samples are assumed to represent the adverse outcome (e.g., missing = drug positive) and in which missing data will be ignored (missing = missing). The “missing positive” method is more conservative and will be considered the primary method.

Primary Outcomes. The effects of the intervention relative to the control group on the dichotomous monthly adherence measure will be analyzed with a longitudinal logistic regression model with treatment group and time as covariates. The group term, representing the between-group difference averaged over time, will be the primary coefficient of interest. Correlation among outcomes over time within individuals will be handled using the method of Generalized Estimating Equations (GEE). The dichotomous viral load variable (<400 HIV-RNA/mL, y/n) will be modeled with an analogous model but with only two follow-up measures.

Secondary and Exploratory Analyses. Continuous measures assessed repeatedly over time (bottle openings, CD4, HIV-1 RNA, and MOS-HIV) will be analyzed using a longitudinal linear regression model, analogous to that used for the primary outcomes. We will control for baseline values in the CD4, viral load, and MOS-HIV models. Measures assessed only at intake will be analyzed via linear or logistic regression as appropriate. Baseline predictors of response to treatment, including positive urine screen for cocaine or opioids, health literacy (TOFHLA), depression (BDI), psychological factors (SCL-90), job and educational history (VEA), and executive function (Wisconsin Card Sorting) will be assessed by fitting regression models with interactions between treatment assignment and each predictor variable, to determine if the effect of treatment on outcome varies as a function of each of these predictors. Similar models, with an interaction between treatment group and drug use, adherence to buprenorphine/methadone, and attendance to primary care, respectively, (as time-varying covariates) will allow us to determine whether these variables affects response to treatment.

Usage, Acceptability, and Cost. Acceptability and SUMI global scale scores, app uses per day, daily duration of use, and cost of the app and incentives and ICER will be summarized via descriptive statistics (mean, SD, medians, histograms).

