### Design

This randomized controlled pilot study features a parallel group design. Participants (N = 50) will be randomly assigned to one of the two groups: Treatment as usual (TAU) or the SteadyRx-supported antiretroviral adherence group (SteadyRx). We will randomize using urn stratification to promote equal numbers of individuals in each group and balanced distributions within a dichotomized covariate expected to be associated with the outcome. Stratification variables are current depression (Y/N); self-report of problem drug use in the last 30 days (Y/N); and TOFHLA score  $\leq$  the rolling median (Y/N). Study participation will last for six months from the date of randomization.

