### Procedures

**Overview.** All staff will be prepared for the intake assessment. After the informed consent is signed by the participant, the Outreach Coordinator notifies the WMU staff and brings the participant to the computer terminal. Student investigators will have the primary responsibility for randomly assigning participants to one of the two study conditions. After completing the randomization procedure, the Outreach Coordinator and WMU staff should train participants how to use the SteadyRx app and PillWatch function (if in SteadyRx group), distribute CTPayer card, and update relevant data logs.

**Randomization Variables.** The proposed pilot study will feature a 2 group, randomized controlled, parallel group design. In order to assess the effectiveness of the proposed intervention as a whole, participants will be assigned to receive usual care (Control Group) or the SteadyRx smartphone intervention. A computerized urn randomization procedure will be used to randomize participants and balance groups on three baseline characteristics that may independently influence the main outcome measures of ART adherence and viral load. Specifically, depression, active drug use, and low health literacy have all been shown to be associated with reductions in ART adherence. Thus, we will use presence of current depression (Y/N); self-reported recent Cocaine or Opiate use (Y/N); and TOFHLA (a health literacy measure; see Assessments) score  $\leq$  the rolling median (Y/N) as the stratification variables in the present study. While it might be desirable to stratify on additional variables, increasing the number of variables is not practical given the study's sample size.

**Procedure.** After obtaining informed consent, the student investigator will complete the intake interview. First, the ASI-Lite will be administered to finish determining eligibility. If the participant is eligible for the study, the TOFHLA will be administered. While the participant is completing the ASI-Lite and the TOFHLA, the student investigator will call the Outreach Coordinator to obtain depression status, CD4 count, HIV-1 RNA levels, and drugs of abuse history information. Once the participant has completed the TOFHLA and information regarding recent drug use and depression status, group assignment can be determined. The student investigator will then call the principal investigator,

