[name], and give the answers to the stratification variables. The principal investigator will then run the urn randomization procedure and relay the group assignment to the student investigator. The participant will then complete the rest of the surveys (Visual Analog Scale for self-reporting ART adherence, MOS-HIV, Patient Reactions Assessment, SteadyRx Reminder Enrollment Form, and Contact Information Sheet).

**Notifying Outreach Coordinator.** After the participant has been randomized and is completing the rest of the assessments (see above), the student investigator will inform the Outreach Coordinator of the group assignment. The Outreach Coordinator will bring the necessary materials to complete the intake to the participant (MEMS cap, CT Payer card, and smartphone (if in SteadyRx group). After the Outreach Coordinator is notified of study condition, and the assessments are finished, the student investigator will inform the participant of study condition.

**Notifying Participant of Study Condition.** The student investigator will notify the participant of the result of the randomization procedure.

If the result is the SteadyRx group, the student investigator will say the following:

“You have been assigned to the SteadyRx group. This means that you are able to be paid \$30 each month for coming here and completing an interview with our outreach staff. This also means that you will be provided with a cell phone for 6 months. You will be provided with a medicine cap that will go on top of your prescription HIV medication bottle. You are responsible for keeping track of both of these items. If either of these items are lost, stolen, or sold, you will be penalized. If you keep your cell phone for the whole study, you will receive \$100 at the end of the study. Instead of receiving \$100 for returning the cellphone, you may choose to keep it. Each time you bring your medicine cap back to an interview, you will receive \$20. On the cell phone, you will find an app called SteadyRx, which we will teach you how to use now. Do you have any questions?”

If the result is the control group, then the student investigator will say the following:

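### As written, the literacy covariate in the adjusted models is a moving-median flag that depends on enrolment order; the TOFHLA score already collected is more informative, though the gain is small

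*Combined protocol and SAP*

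**What the plan says.** The Abstract (Design) describes urn randomisation intended to give "balanced distributions within a dichotomized covariate expected to be associated with the outcome". The section on random assignment (Procedures, Randomization Variables) names three binary factors: current depression, recent drug use, and whether the TOFHLA score lies at or below "the rolling median (Y/N) as the stratification variables in the present study".

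The same section shows that the full score exists before allocation: "If the participant is eligible for the study, the TOFHLA will be administered". The codes are then passed on one participant at a time: "The principal investigator will then run the urn randomization procedure and relay the group assignment to the student investigator".

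The opening paragraph of the Analytic plan carries these factors into the models: "All analyses will be adjusted for the pre-specified covariates used for stratification". Nothing in the documents re-codes the literacy factor at a fixed cut-off for analysis or puts the score in its place.

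Two other places bear on the point. The secondary and exploratory analyses use TOFHLA as an effect modifier without saying whether as score or split. The section on data analysis for a future publication fits GEE models with and without the stratification variables, and presents the adjusted model by default.

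**The concern.** A moving cut-off is workable for sequential allocation, because the urn needs only a code at the moment of assignment. As a regression covariate it is awkward. A participant who follows mostly lower scorers is coded above the median; another with the identical score who follows mostly higher scorers is coded at or below it. The coefficient then describes no fixed level of literacy.

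The protocol gives its own reason to care: it lists low health literacy among the characteristics associated with poorer ART adherence. If so, a covariate that tracks literacy loosely gives up part of the benefit of adjustment and corrects less of any chance imbalance between two groups of about 25. What is at stake is efficiency and a clear covariate definition, not the validity of the test.

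**Working it through.** **Inputs from the documents.** N = 50 in two groups; the literacy flag, fixed participant by participant before assignment; the full TOFHLA score collected before assignment; two-sided tests at 0.05; logistic GEE for the monthly adherence outcome.

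**Not in the documents, so assumed.** The TOFHLA distribution, its relation to outcome, the treatment effect and the event rates. The plan gives no power figure, so there is nothing to reproduce first.

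**Step 1: how often the coding is inconsistent.** In 4,000 simulated sequences of 50 scores, each score was coded against the median of the scores so far, with and without the participant's own score. Three score shapes were tried: rounded normal, ceiling-skewed and coarse integer.
- Chance that at least one identical score is coded both ways: 0.88 to 0.94.
- Chance that some higher score is coded low while a lower one is coded high: 0.77 to 0.85.
- Participants coded differently from a split at the final median: about 4 of 50 on average.

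**Step 2: information kept.** For a normal score split at its true median, the correlation between score and indicator has size φ(0)/0.5 = 0.399/0.5 = 0.798, so the share of variance kept is 0.798² = 2/π = 0.637. The simulation gave 0.637 for the final-median split and 0.578 to 0.584 for the rolling flag. Taking 0.578:
- total loss: 1 − 0.578 = 0.422
- loss from dichotomising: 1 − 0.637 = 0.363
- extra loss from the moving cut-off: 0.637 − 0.578 = 0.059, or 0.059/0.422 = 14% of the total

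Across the three score shapes the rolling flag kept 53% to 61% and the final-median split 60% to 67%.

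**Step 3: validity.** With a linear outcome and urn allocation on the flag alone (4,000 runs per setting), type I error was 0.045 to 0.052 with the flag and 0.046 to 0.052 with the score. The simulation error at 0.05 is √(0.05 × 0.95/4,000) = 0.003, so neither departs from 0.05.

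**Step 4: linear outcome.** Assumed treatment effect 0.8 SD.

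| Score–outcome correlation | Power, flag | Power, score | Gain (points) | Fall in SE |
|---|---|---|---|---|
| 0.2 | 0.786 | 0.790 | 0.4 | 0.4% |
| 0.3 | 0.808 | 0.824 | 1.6 | 1.7% |
| 0.5 | 0.844 | 0.884 | 4.0 | 5.9% |

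**Step 5: the planned type of primary model.** Logistic GEE, six monthly binary outcomes, N = 50. The literacy effect is in log-odds per SD of TOFHLA.

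Simulation A: independence working correlation, robust SE, three covariates, conditional treatment log-odds ratio 1.4, 4,000 runs per setting.

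| Literacy effect | Mean SE, flag / score | Power, flag / score | Gain (points) |
|---|---|---|---|
| 0.3 | 0.403 / 0.404 | 0.718 / 0.719 | 0.1 |
| 0.6 | 0.409 / 0.409 | 0.696 / 0.713 | 1.7 |
| 0.9 | 0.418 / 0.417 | 0.670 / 0.705 | 3.5 |

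Simulation B: exchangeable working correlation, urn on the literacy flag alone, conditional treatment effect 1.0, random-intercept SD 1, 400 runs per setting.

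| Literacy effect | Power, flag / score | Gain (points) |
|---|---|---|
| 0.4 | 0.715 / 0.720 | 0.5 |
| 0.8 | 0.675 / 0.745 | 7.0 |
| 1.2 | 0.582 / 0.675 | 9.3 |

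B is the noisier: each power figure has a simulation error of about √(0.7 × 0.3/400) = 0.023. On the odds-ratio scale, 0.3 to 0.6 is exp(0.3) = 1.35 to exp(0.6) = 1.82 per SD, and 0.8 to 1.2 is 2.23 to 3.32. The larger gains therefore need literacy to more than double the odds of adherence per SD. Simulation A shows almost no change in SE; the gain comes mainly from a larger conditional coefficient. Type I error was 0.047 to 0.054 in A for both covariates, and 0.055 (flag) against 0.048 (score) in B.

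**The case against.** Adjusting for an allocation factor in the form used for allocation is a recognised, objective convention, and this flag is fixed before assignment. That stands: the plan's analysis is valid.

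The variance percentages are not themselves effects on the trial, and the moving cut-off accounts for only about 6 of the 42 points lost. That also stands. The count of about 4 in 50 compares the flag with a final-median split, which has no special claim to be correct; it measures instability, not error.

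The Analytic plan does not spell out how the stratification covariates are coded in the models. The as-randomised flag is the natural reading, but it is a reading. This makes an explicit statement more useful. The models fitted without the stratifiers, in the section on a future publication, do not remove the point, since that section presents the adjusted results by default.

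Two stronger readings are tempting and should not be drawn:
- A reader might infer that an order-dependent covariate biases the treatment effect or invalidates the test. The code is set before assignment, and type I error stays near 0.05.
- A reader might infer that ties at the top score would put nearly everyone in the low category. In simulation, 59% are coded low if 40% tie at the maximum, and 97% if 70% tie. The documents give no TOFHLA distribution, so this is hypothetical. Heavy ties would also strain a linear score term.

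**Conclusion.** The point holds as a modest improvement to a valid plan. The literacy covariate, as written, depends on enrolment order and carries less information than a score already in hand.

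For the primary logistic GEE, a gain of roughly 0 to 4 power points is a fair summary for weak to moderate literacy effects. Larger gains, up to about 9 points in the smaller simulation, need a strong effect. For linear secondary outcomes the gain was also 0 to 4 points at correlations of 0.2 to 0.5, there with a somewhat smaller SE.

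These sizes rest on assumed score distributions, literacy effects and treatment effects, and on a literacy effect that is linear on the model's scale. The simulations also simplified the three-factor urn. None of these inputs can be checked against the documents.

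**What to change.** Keep the urn unchanged. In the opening paragraph of the Analytic plan, specify the continuous TOFHLA score in place of the rolling-median flag in the adjusted models, and retain the depression and drug-use indicators. Report the model with the as-randomised flag as a sensitivity analysis. The number of parameters stays the same and no new data are needed.

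The section on a future publication is written in the past tense. If outcome data have already been analysed, changing the main covariate would be post hoc. In that case keep the planned adjustment, state that the flag is used as randomised, and add the score-adjusted model as a labelled sensitivity analysis.

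The cost is a short text change and one extra model per outcome. The downsides are the assumed linear score effect and a covariate that no longer matches the urn factor exactly.

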## Primary Outcome Variable

The primary outcome measures for intervention effectiveness will be (1) the percent of participants who take 95% of prescribed doses of their antiretroviral medication(s) within three hours of their scheduled dosing time each month as measured by MEMS, and (2) the percent of participants who achieve a viral load <400 HIV-RNA/mL at each of the two assessments collected during the active intervention period.

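### The plan names two primary effectiveness outcomes but gives no success rule, testing order or alpha split; if either alone can carry the claim, the false-positive rate is up to 9.75%

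*Combined protocol and SAP*

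**What the plan says.** Under Primary Outcome Variable the plural is explicit: "The primary outcome measures for intervention effectiveness will be (1) the percent of participants who take 95% of prescribed doses" on time each month, recorded with the MEMS cap. The second primary measure is listed as "2) the percent of participants who achieve a viral load <400 HIV-RNA/mL at each of the two assessments collected during the active intervention period".

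The Analytic plan for SteadyRx study gives each outcome its own longitudinal logistic model fitted by GEE. For adherence, "The group term, representing the between-group difference averaged over time, will be the primary coefficient of interest". Viral load "will be modeled with an analogous model but with only two follow-up measures". On error control it says "All hypothesis tests will be two-sided". It sets alpha at 0.05 and adds that "p-values for secondary analyses will be corrected to maintain" that level. It has no corresponding provision for the primary analyses.

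Two other places bear on which outcome leads. The same analytic plan speaks in the singular of "the automated collection of our primary outcome measure". The Secondary Outcome Variables section also refers to a single primary measure, dichotomized adherence, and ranks it as clinically the most important. Neither place sets a formal hierarchy.

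The closing section, Data Analysis to be reported in future publication, is written in the past tense. It keeps alpha at .05, mentions no correction, and leaves out the biometric variables because of a data collection error.

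**The concern.** With two primary outcomes, two tests and one nominal level, the meaning of 0.05 depends on what counts as success. If the trial may be called positive when either outcome is significant, 0.05 is the error rate of each test but not of the trial's main claim. The plan recognises multiplicity, since it corrects the secondary p-values, yet it leaves the primary pair uncovered. A report could then present whichever primary outcome reached significance as the trial's effectiveness result, and a reader could not tell from the plan whether that was the intended rule.

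**Working it through.** **Inputs from the documents.** Two primary outcomes (Primary Outcome Variable). One test for each, the GEE group term; two-sided; alpha 0.05; correction for secondary analyses only (Analytic plan).

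**Inputs not in the documents.** The correlation between the two test statistics is not given, so a range is assumed. Each test is taken to have exactly its nominal 5% size and the pair to be jointly normal.

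**Step 1: the plan's own figure.** Alpha of 0.05 is a chosen level, not a derived one. A single test gives 1 − 0.95 = 0.05. The plan states no rate for the two primaries together, so there is nothing further to reproduce.

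**Step 2: either outcome suffices, independent tests.** 1 − 0.95² = 1 − 0.9025 = 0.0975. Whatever the dependence, the rate cannot exceed 0.05 + 0.05 = 0.10.

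**Step 3: either outcome suffices, correlated tests.** The rate is 1 − P(|Z1| < 1.96 and |Z2| < 1.96), with both null hypotheses true. Counting only false findings of benefit, it is 1 − P(Z1 < 1.96 and Z2 < 1.96), against 2.5% for one test. With independence this is 1 − 0.975² = 0.0494.

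**Step 4: both outcomes required.** With both nulls true, P(both significant) = 0.10 − P(at least one significant). For example, 0.10 − 0.0907 = 0.0093 at correlation 0.5.

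| Assumed correlation | At least one significant, two-sided | At least one, benefit direction only | Both significant |
|---|---|---|---|
| 0 | 9.75% | 4.94% | 0.25% |
| 0.3 | 9.51% | 4.76% | 0.49% |
| 0.5 | 9.07% | 4.54% | 0.93% |
| 0.7 | 8.35% | 4.17% | 1.65% |
| 0.9 | 7.04% | 3.52% | 2.96% |

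The two-sided rate falls below 9% once the correlation exceeds about 0.53. Under a both-required rule, a false claim needs a true null to be rejected at 0.05, so the rate is at most 5% even when only one null is true.

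**Step 5: the remedies.**
- Fixed sequence, MEMS first. If the MEMS null is true, any false claim requires rejecting it, which happens at most 5% of the time. If it is false, the only possible error is on viral load, again at most 5%.
- Bonferroni at 0.025 each: 1 − 0.975² = 4.94% if independent, 4.65% at correlation 0.5.
- Holm also holds 5%. Its cost for an outcome with 80% power at 0.05, at the 0.025 step: Φ(1.960 + 0.842 − 2.241) = Φ(0.561) ≈ 0.71.

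**The case against.** The strongest reply is that the inflation rests on a rule the documents never state. A reader might infer that the trial's error rate simply is 9 to 10%. The text does not support that: it nowhere says that one outcome is enough, and a both-required rule would give no inflation. Adherence and viral load are also likely to be positively correlated, which lowers the rate. This stands, and the figure must be conditional. But no both-required rule is written either, and even at a correlation of 0.9 the either-outcome rate is 7.0%.

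Second, the two-sided figure counts false findings of harm as well as benefit. False benefit alone is about 4.9% at correlation 0 and 4.5% at 0.5. That is correct and should be disclosed, though against 2.5% for one test it is still close to double.

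Third, a reader might infer that the published analysis carries this inflation. If the omitted biometric variables include viral load, which is the natural reading though not spelled out, only the MEMS primary test remains, at 5%. This limits the practical effect. It does not supply a rule, or say how the claim stands once one of two named primaries is lost.

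Fourth, it would be too strong to say that the documents give no hint of which outcome leads. The stated purpose is adherence, the cost-effectiveness ratio uses the adherence outcome, and Secondary Outcome Variables ranks dichotomized adherence highest. These hints point to MEMS, but they are not a testing order.

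Finally, this is a pilot with 50 participants, and a larger study is foreseen. That lowers the stakes, but the plan still labels these outcomes as measures of effectiveness and sets formal tests.

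**Conclusion.** The point holds in conditional form. The plan has two primary outcomes, each tested at two-sided 0.05, and no success rule, order or alpha split. If either outcome alone may support the claim, the chance of at least one false significant primary is 9.75% with independent tests and lower with correlation. The benefit-only equivalent is about half of that, against 2.5%. These figures assume that both nulls are true, that each GEE test has its nominal size, and that the statistics are jointly normal; every correlation is an assumption.

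The finding concerns the analytic plan. It does not show an inflated rate for the single MEMS test that appears to remain in the published analysis. For a pilot the consequence is moderate, but the rule should be stated.

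**What to change.** State a fixed sequence in the Analytic plan, in line with the ranking in Secondary Outcome Variables: *MEMS adherence is tested first at two-sided 0.05; viral load is tested at two-sided 0.05 only if MEMS is significant, and is otherwise reported descriptively.* This holds the primary error rate at 5%, takes no power from the MEMS test, and still works if viral load cannot be analysed. The cost is that viral load can never support a claim on its own.

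If Holm is preferred, the condition must be explicit: *the smaller p-value is compared with 0.025 and, only if that is significant, the larger with 0.05.* With p-values of 0.03 and 0.04, Holm rejects neither; without the condition, the larger would be declared significant. Holm takes 80% power to about 71% at the 0.025 step. It would also need a statement of the level for MEMS if viral load is unavailable.

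Because the section on the published analysis is in the past tense, a sentence added now may not count as prespecification. Any rule adopted after results were seen must be labelled post hoc. Either way, the report should say that two primaries were planned, which of them were analysed, and that the plan contained no multiplicity rule for them.
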